10.1.4 Definition

A serious adverse event (SAE) is any adverse event (experience) that in the opinion of either the investigator or sponsor results in **ANY** of the following:

- Death.
- A life-threatening adverse event (experience). Any AE that places a participant or participants, in the view of the Investigator or sponsor, at immediate risk of death from the reaction as it occurred. It does NOT include an AE that, had it occurred in a more severe form, might have caused death.
- Inpatient hospitalization or prolongation of existing hospitalization (for > 24 hours).
- A persistent or significant incapacity or substantial disruption of the ability to conduct normal life functions.
- A congenital anomaly or birth defect.
- Important Medical Event (IME) that, based upon medical judgment, may jeopardize the participant and may require medical or surgical intervention to prevent one of the outcomes listed above.

10.1.5 Reporting Serious Adverse Events

All new SAEs occurring from the date the participant signs the study consent until 30 days after the last intervention or a new treatment is started, whichever comes first, will be reported. The principal investigator or designee will inform Roswell (via email using both the Oncore SAE form and MEDWATCH 3500A form) within twenty-four (24) hours of first awareness of any event that meets the above criteria. Forms will be submitted to [contact]. See Appendix C for Multi-site reporting instructions. SAEs occurring after the 30 day follow-up period that the investigator determines to be possibly, probably or definitely related to the study intervention should be reported.

SAEs that are unexpected and possibly, probably or definitely related must be reported as an Unanticipated Problem. Please refer to **Section 0** for details on reporting Unanticipated Problems.

Follow-Up for Serious Adverse Events

All related SAEs should be followed to their resolution, until the study participant is lost to follow-up, the start of a new treatment, or until the study investigator assesses the event(s) as stable or irreversible. New information will be reported when it is received.

Unanticipated Problems

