8.1.8 Initial Follow-Up Evaluation

The following evaluations will be performed **4 weeks** (± **1 week**) after the last study I-PDT and/or PDT (*unless otherwise indicated**):

- Physical examination (including vital signs)
- Hematology: Complete blood count (CBC) with automated differentials.
- Chemistry: Complete metabolic panel (CMP).
- Blood draw for immune markers
- ECOG Performance Status (Appendix A)
- Tumor/Disease Assessment: Chest CT scan
- Concomitant medications
- Quality of Life Questionnaire (Cohorts A and B; Appendix D)
- Adverse events (will be followed for 30 days following treatment/procedure)
- Schedule date/time for follow-up bronchoscopy with EBUS (without TBNA). TBNA will be performed only if clinically indicated outside the scope of this study. If a tumor is visible, tumor tissue biopsies (about 50-300 mg per biopsy, if feasible) will be collected for immune markers. NOTE: The bronchoscopy will not be performed at this visit.
- If EBUS is performed and a tumor is visible, tumor tissue biopsies (about 50-300 mg per biopsy, if feasible) will be collected for immune markers.

*Bronchoscopic and ultrasound images that are routinely obtained during therapeutic procedures will be used to evaluate the airway initially and during follow up. *Note: Initial follow-up bronchoscopy will be performed within 4 weeks following the first follow-up visit. Additional bronchoscopies will be performed as clinically indicated.*

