10.1.3 Reporting Adverse Events

Table 2Guidelines for Routine Adverse Event Reporting for Phase 2 Studies
(Regardless of Expectedness)

Routine AEs occurring between the start date of intervention until 30 days after the last intervention, or until the event has resolved, the study participant is lost to follow-up, the start of a new treatment, or until the study investigator assesses the event(s) as stable or irreversible, will be reported. New information will be reported after it is received.

Adverse events will be graded from 1 to 5. Mild and moderate side effects are common after therapeutic bronchoscopy for central airway tumors. Therefore, grade 3 or above will be included in safety analysis, and grades 1 and 2 will be collected and reported.

Serious Adverse Events

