12.1.9 Safety Monitoring Lead-In (Cohort B)

The safety profile will be measured by recording treatment related AEs that are \geq grade 4 with attribution of 'possible', 'probable', or 'definite', according to the NCI CTCAE v5.0. The safety measures will be evaluated in all patients who received image-guided I-PDT preceded by standard of care p-XRT of 8 Gy x1 for the treating their MCAO. The following decision rules will be followed: (i) If 0/3 AE \geq grade 4's are observed it will be concluded the therapy is safe. (ii) If 1/3 AE \geq grade 4's are observed, enroll 3 more patients for safety evaluation. If 1/6 AE \geq grade 4's are observed it will be concluded the therapy is safe. If \geq 2/6 AE \geq grade 4's are observed it will be concluded that therapy is unsafe. We calculated via Monte Carlo simulation that if the AE \geq grade 4 rate is 20%, 30% and 40% the respective probabilities of declaring the treatment unsafe are 0.26, 0.51 and 0.70.

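### A related SAE that occurs after an early change of therapy but by day 30 is required by neither reporting clause of Section 10.1.5, and could go uncounted in the Cohort B safety lead-in

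*Combined protocol and SAP*

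**What the plan says.** Section 10.1.5 collects new SAEs from consent "until 30 days after the last intervention or a new treatment is started, whichever comes first, will be reported". A second clause asks for "SAEs occurring after the 30 day follow-up period that the investigator determines to be possibly, probably or definitely related to the study intervention". A third states that "SAEs that are unexpected and possibly, probably or definitely related must be reported as an Unanticipated Problem". The follow-up paragraph under the same heading lets follow-up of a related SAE end when a new treatment starts.

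Section 10.1.3 sets the routine AE window at 30 days after the last intervention, then adds "or until the event has resolved, the study participant is lost to follow-up, the start of a new treatment" and an investigator judgement that the event is stable or irreversible.

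Section 8.1.8 has no such cut-off: "Adverse events (will be followed for 30 days following treatment/procedure". Item 7 of Appendix C asks sites to report every SAE, related or not, and gives no window.

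Section 12.1.9 begins "The safety profile will be measured by recording treatment related AEs" and counts those of grade 4 or higher attributed as possible, probable or definite. It gives no observation period. None of these sections defines a new treatment.

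**The concern.** The late clause is tied to day 30 and not to the point at which collection actually stopped. When collection stops early, an interval opens in which Section 10.1.5 does not ask for related SAEs, yet they become reportable again after day 30. Nothing in the documents explains why the earlier event should matter less. Section 1.1.4 says the photosensitizer may stay in the tumor for at least 30 days, so harm from the study treatment remains plausible throughout the interval.

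What is at stake is mainly the Cohort B lead-in. Section 6.1.10 says the risk of I-PDT two days after palliative radiotherapy is unknown, and the lead-in judges that combination on 3 to 6 patients. With so few patients, a single uncounted event can change the decision. The conflict between sections also means that sites could collect different data while each follows the protocol.

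**Working it through.** **Step 1. The two clauses of 10.1.5.** Count days from the last study intervention. Let D be the day of a related SAE and N the day a new treatment starts.

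- Main clause: requires a report if D ≤ min(30, N).
- Late clause: asks for a report if D > 30.
- Covered by neither: N < D ≤ 30.

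Example with N = 10. For D = 20, min(30, 10) = 10 and 20 > 10, so the main clause does not apply; 20 is not above 30, so the late clause does not apply. For D = 35, the late clause applies.

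**Step 2. Other routes that could capture the day-20 event.**

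| Route | New-treatment cut-off? | What it captures |
|---|---|---|
| 10.1.3, routine AEs | Yes, listed among the end points | Unclear: the list mixes collection of new events with follow-up of known ones |
| 8.1.8, initial follow-up | No | AEs for 30 days |
| Appendix C, item 7 | No window at all | All SAEs at sites |
| 10.1.5 to 10.1.7, Unanticipated Problems | None stated | Unexpected related SAEs, including those unexpected by severity |
| 8.1.10 and Table 1, survival status | No | Deaths to 24 weeks |

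The clearest remaining loss is an event that is related, expected in nature and severity, and non-fatal.

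**Step 3. The Cohort B lead-in.** Inputs from 12.1.9: 0/3 is safe; 1/3 adds three patients; then 1/6 is safe and 2 or more of 6 is unsafe. Two or more of the first three is treated here as unsafe, since 2/6 is then already reached. With p the true rate per patient of a qualifying event:

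P(unsafe) = 1 − (1−p)³ − 3p(1−p)⁵

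At p = 0.30: 1 − 0.343 − 3 × 0.30 × 0.16807 = 1 − 0.343 − 0.151 = 0.506.

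For a share m of qualifying events never counted (assumed the same for every patient and independent of other events), replace p by p(1−m). At p = 0.30 and m = 0.10 the effective rate is 0.27: 1 − 0.389 − 3 × 0.27 × 0.2073 = 1 − 0.389 − 0.168 = 0.443.

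| True rate | Stated in 12.1.9 | Exact, m = 0 | m = 5% | m = 10% | m = 30% |
|---|---|---|---|---|---|
| 20% | 0.26 | 0.291 | 0.270 | 0.248 | 0.166 |
| 30% | 0.51 | 0.506 | 0.475 | 0.443 | 0.313 |
| 40% | 0.70 | 0.691 | 0.657 | 0.622 | 0.464 |

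The plan's figures at 30% and 40% are reproduced to within 0.01. The figure at 20% is not (0.291 against 0.26). A small simulation might explain that: with 200 runs the standard error is about 0.03. It should be rechecked, but this point does not depend on it.

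**Step 4. One event, with no assumption about m.** Removing one qualifying event turns 1/3 (enroll three more) into 0/3 (safe, no expansion), and 2/6 (unsafe) into 1/6 (safe).

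**The case against.** The strongest reply is that the gap in 10.1.5 matters little because other provisions cover it. Four parts of that reply carry weight.

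- **Unanticipated Problems.** A reader might infer that a grade 4 airway bleed is necessarily lost because Section 6.1.10 lists bleeding as a risk. The documents do not support that. Sections 10.1.1 and 10.1.6 define unexpected by severity as well as by nature, and 6.1.10 lists bleeding without a grade. Such an event may well have to be reported, with no new-treatment cut-off. The limit is that this route depends on judgement and leads to the IRB; 12.1.9 does not say that it feeds the lead-in count.
- **8.1.8 and Appendix C.** Followed as written, they would recover many of these events. But they contradict the section that governs SAE reporting, and nothing says which prevails. That is a reason to reconcile the text, not to leave it.
- **The link to the lead-in.** 12.1.9 counts AEs, not SAEs, and does not adopt the window of 10.1.5. The link runs through 10.1.3, whose list can be read as describing how long a known event is followed, not when collection of new events ends. This stands, so the effect on the lead-in is conditional.
- **Frequency.** A reader might infer that changing therapy within 30 days is common in this population. The documents give no rate, and their references to chemotherapy concern patients already receiving it. This stands too.

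**Conclusion.** The gap in 10.1.5 is there on a literal reading, and the conflict among 8.1.8, 10.1.3, 10.1.5 and Appendix C needs no assumption. The potential loss is narrower than all severe related events: it is clearest for related, expected, non-fatal events after a new therapy starts and by day 30.

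Whether the lead-in is affected depends on whether 12.1.9 uses these collection rules, which it does not say. If it does, one uncounted event is enough to change the decision path. The fall from 0.51 to 0.44 at a true 30% rate rests on an assumed 10% loss, and every value of m in the table is likewise an assumption. A reader might conclude that the safety tables are biased low. The documents show how that could happen, not that it will, and they give no basis for its size.

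This should be fixed: the change is cheap and protects a small safety decision. It does not invalidate the design.

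**What to change.** - Align 8.1.8, 10.1.3, 10.1.5 and Appendix C so that all AEs and SAEs are collected through 30 days after the last study intervention, whatever other therapy is started.
- Record the start date of any new therapy and let the existing attribution categories in 10.1.2 deal with confounding.
- Reword the late clause to cover SAEs judged at least possibly related that occur after collection ends, whatever ended it.
- Remove a new therapy as a reason to end follow-up of a related SAE.
- State in 12.1.9 that each lead-in patient is assessed over the full 30 days.

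The cost is protocol wording, with no change to sample size, significance level or visit schedule. The initial follow-up visit at 4 ± 1 weeks can fall between day 21 and day 35, so a patient seen before day 30 would need a brief later check to complete the window. More events caused by other therapy will be recorded and will need attribution.

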10.1.6 Definition

An Unanticipated Problem (UP) is any incident, experience, or outcome that meets all of the following criteria:

- Unexpected (in terms of nature, severity, or frequency) given:
 - The research procedures that are described in the study-related documents, including study deviations, as well as issues related to compromise of participant privacy or confidentiality of data.
 - The characteristics of the participant population being studied.
- Related or possibly related to participation in the research (possibly related means there is a reasonable possibility that the incident, experience, or outcome may have been caused by the procedures involved in the research).
- Suggests that the research places participants or others at a greater risk of harm (including physical, psychological, economic, or social harm) than was previously known or recognized or if in relation to an AE is deemed Serious per Section 0.

10.1.7 Reporting Unanticipated Problems

Unanticipated problem reporting will begin at the time of participant consent. The Reportable New Information Form will be submitted to the CRS Quality Assurance (QA) Office within 1 business day of becoming aware of the Unanticipated Problem. After review, the CRS QA Office will submit the RNI to the IRB.

When becoming aware of new information about an Unanticipated Problem, submit the updated information to CRS QA Office with an updated Reportable New Information Form. The site Investigator or designated research personnel will report all unanticipated problems to the **IRB in accordance with their local institutional guidelines**.

11 DATA AND SAFETY MONITORING

The Roswell Park Data and Safety Monitoring Committee (DSMC) will assess the progress of the study, the safety data, and critical efficacy endpoints. The DSMC will review the study annually and will make recommendations that include but not limited to; (a) continuation of the study, (b) modifications to the design, (c) suspension of or, (d) termination of the study.

12 STATISTICAL METHODOLOGY

This is a multi-center, multi-arm, Phase I (Cohort 0, data collection completed) and Phase II study [Cohort A (8 already enrolled under Phase 1 portion of Cohort A from previous protocol version) and Cohort B]. Cohort 0 is closed to accrual and fulfilled the Phase 1 safety monitoring requirements. Cohort 0 provided the safety monitoring component for Cohort A of this Phase II study. Cohort 0 consisted of patients with the diagnosis of lung cancer that received porfimer sodium with EBUS I-PDT and all of the study procedures with the exception of the Quality of Life Questionnaires and Six Minute Walk Test. Cohort A consists of patients with the diagnosis of lung cancer or other malignancies causing airway obstruction, or cancer that is not a candidate

for surgery or curative radiation therapy; EBUS I-PDT; and all of the study procedures. Cohort B will consist of patients with the diagnosis of lung cancer or other malignancies causing airway obstruction, or cancer that is not a candidate for surgery or curative radiation therapy. Subjects in Cohort B will receive the EBUS guided I-PDT 48 ± 4 h after standard of care palliative radiotherapy of 8 Gy x1.

The primary safety endpoints for Cohort 0 for this study are:

• AEs that are \geq Grade 4.

The primary efficacy endpoints for Cohort A and Cohort B portion of this study are:

- Objective tumor response (CR, PR, PD, and SD)
- The FACT-L Total Score related subscale
- 6-Minute walk measures

The secondary endpoints for Cohort 0+A and Cohort B of this study are:

- The number of bronchoscopies
- Progression free survival
- Compare the treatment plan in DOSIE[™] with the plan generated in COMSOL[™] in Cohort A only.
- Measure changes in optical properties and irradiance and fluence and relationship to response.

The exploratory endpoints are for Cohort 0+A and Cohort B of this study:

- Porfimer sodium retention in the target tumor tissue
- The relationship between immune biomarkers and response

12.1.1 Demographics and Baseline Characteristics

Descriptive statistics (as appropriate: n, percent, mean, median, minimum, and maximum) will be used to summarize demographic and baseline characteristics.

12.1.2 Primary Cohort 0 Phase I Safety Analysis

For patients LALC or other malignancies in the central airway that may extend and involve the esophagus. For Cohort 0, the safety profile will be measured by recording I-PDT and/or PDT treatment related AEs that are \geq grade 4 with attribution of 'possible', 'probable', or 'definite', according to the NCI CTCAE v5.0. The safety measures will be evaluated in all patients who received I-PDT and/or PDT following bronchoscopic intervention for malignant airway obstruction. Let *p* represent the proportion of the evaluable population of interest who experience an AE \geq grade 4. A true response of more than $p_0=0.20$ is considered unacceptable and evidence of such will deem the treatment unsafe for further study.

The null and alternative hypotheses to be tested are:

$$\begin{split} H_0: p &\leq p_0, \\ H_a: p > p_0. \end{split}$$

The study design stops early for evidence of safety and will proceed in two stages:

- Stage 1: If 0 out of the first 3 evaluable participants have an I-PDT and/or PDT treatment related AE≥ grade 4 (with attribution of 'possible', 'probable', or 'definite'), it will be concluded that the therapy is safe and the study will enter the Phase II component. Otherwise, the study will progress to the second stage.
- Stage 2: We will accrue 3 additional evaluable participants. If 3 or more of the total of 6 evaluable participants will have I-PDT and/or PDT treatment related AE≥ grade 4 (attribution of 'possible', 'probable', or 'definite'), it will be concluded that *p* exceeds and that the therapy is unsafe; otherwise, it will be concluded that the therapy is safe and enter the Phase II component.

The nominal significance level of this design is α =0.10.

12.1.3 Primary Phase II Efficacy Analysis

The primary endpoint for Cohort A and Cohort B is the proportion of complete responders (CR) and partial responders (PR) as measured by RECIST v1.1 at 12 ± 1 week after DOSIETM (Cohort A) and COMSOLTM guided I-PDT.

For Cohort A, we hypothesize that the objective tumor response for CR+PR will be at least 29%. We also want to investigate the impact of variation in optical properties, Photofrin® retention, and fiber location perturbation on the objective tumor response. The primary analysis will consist of a one-sided exact binomial test of H₀: π =0.05 versus H_a: π >0.05 at level α =0.05, where π is the proportion of CR+PR responders. For Cohort B, the primary analysis will consist of a one-sided exact binomial test of H₀: π =0.30 versus H_a: π >0.30 at level α =0.05.

Additional clinical efficacy endpoints are: (1) changes from baseline to 3 months in the FACT-L Total Score related subscales (physical well-being, social/family well-being, emotional well-being, functional well-being); (2) the 6-minute walk measures (distance, VO2max, shortness of breath scores). All key clinical efficacy outcomes will be considered suitably continuous will be analyzed with an analysis-of-covariance (ANCOVA) approach regressing change from baseline to three months on the baseline value of the respective measure adjusted for baseline tumor volume, age, and sex.

